Similar to the BPD, we will collect data on a modified SURG-TLX on each of the eligible surgery days. The modified SURG-TLX will be evaluated at the end of each surgery day to assess participant experience throughout the surgery day. The SURG-TLX measures 6 areas: mental demands, physical demands, task complexity, situational stress, and distractions. Each of the 6 areas is rated on a scale of 0 to 100, which is added to generate a sum score. The sum score will then be compared across surgery days with and without the intervention.

Data will also be collected from medical records about each surgery in the study. The following perioperative data will be collected: surgeries performed, operative time, and intraoperative complications (i.e. bladder/bowel injury, large vessel injury, transfusion, allergic reaction, difficulty ventilating, ICU admission).

At the conclusion of the study, an anonymous exit survey will be performed to give all participants an opportunity to provide feedback. Data will be collected on the results of the exit survey. The exit survey will include questions about the participants experience performing the exercises including ease of performing exercises and incorporating into the surgical day.

Randomization

To randomize surgeons, we will first construct Williams squares where exercise follows no exercise (and vice versa) the same number of times.¹⁰ After the Williams squares are constructed and selected, individual sequences are randomly assigned to the surgeon. Sequence randomization will occur according to a predetermined computer-generated scheme prepared by a study statistician.

Statistical Analysis

Descriptive statistics (means, standard deviations, frequencies) will characterize the sample to assess comparability of the intervention and control surgery days. Chi-square test or Fisher's exact test will be used for categorical variables. Continuous variables will be examined for normality using the Shapiro-Wilk test; normally distributed continuous variables will be compared using the Student's t-test and those non-normally distributed will be compared using the Mann-Whitney U test. We will use linear mixed models to test for an association between BPDS and the targeted micro breaks/exercise intervention across surgery days. We will exclude surgeons who do not provide self-reported BPDS data on both days for a certain body part.

Power analysis:

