Sample size estimations were conducted using G*Power. We utilized the research by Park et al (2017) to estimate the effect of intraoperative microbreaks and exercises on surgeon body discomfort. Park et al (2017) reported differences in body discomfort between surgeons who completed the intraoperative microbreaks/exercises and the control group that ranged from $d=0.00$ to $d=0.48$. Using G*Power, we computed the required sample size to detect a medium effect with the specified parameters: **power=0.85, $\alpha=.05$, $f=0.25$, and measurements = 10**. This yielded a total sample size of at least 20 surgeons, where each surgeon completes 10 surgery days with the intervention and 10 surgery days without the intervention, with a minimal total of 20 surgery days.

Table 1. Power and sample size estimations for a within-subject design

Cohen's f	f=0.1 small	f=0.15	f=0.20	f=0.25 medium	f=0.30	f=0.35	f=0.40 large
total sample size	power						
10	0.12	0.23	0.41	0.62	0.8	0.9	1.0
15	0.16	0.36	0.62	0.85	1.0	1.0	1.0
20	0.21	0.49	0.79	0.95	1.0	1.0	1.0
25	0.27	0.60	0.89	0.99	1.0	1.0	1.0

STUDY ELEMENT IDENTIFICATION

6 Study Elements

Click on the check box (or double click and type an "X" if using Google Docs) each procedure included in your study.

A full description of all study procedures should be provided in the Procedures (Details) section below and/or the applicable supplement form.

 Bio-specimens	 Biometrics	 Registry or Repository
 Focus Group	 Genetic Analysis	 Genomic Data Sharing
 International Research	 Interview/Survey	 MRI
 Protected Health Information	 Observation	 Radioactive Material/PET/Nuc. Med
 Record Review	 Sensors (Externally Placed)	 Sensors (Inserted)
 Video/Audio Recording	 X-Ray/CT	

7 Study Intervention

Click on the check box (or double click and type an "X" if using Google Docs) if you will implement any of the following interventions.

A full description of all study interventions should be provided in the Procedures (Details) section below and/or the applicable supplement form.

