This study will recruit at least 20 surgeons. Each surgeon will complete at least 10 surgery days with the intervention and at least 10 surgery days without the intervention, which will yield at least 20 surgery days.

15 Sample size rationale

To input text, click in the light grey area below.

Using G*Power, we computed the required sample size to detect a medium effect with the specified parameters: **power=0.85, $\alpha=.05$, $f=0.25$** , and measurements = 10. This yielded a total sample size of at least 20 surgeons, where each surgeon completes 10 surgery days with the intervention and 10 surgery days without the intervention, with a minimal total of 20 surgery days.

SCREENING AND RECRUITMENT

16 Identification and Screening

Click on the check box (or double click and type an "X" if using Google Docs) if true.

- This study involves obtaining information or biospecimens for the purpose of screening, recruiting or determining eligibility of prospective subjects prior to informed consent by either:
1. Oral or written communication with the prospective subject or LAR
 2. By accessing records containing identifiable private information or stored identifiable biospecimens.

17 Identification and/or Screening Procedures

Describe the identification and/or screening procedures below.

To input text, click in the light grey area below.

Surgeons (residents, fellows, and attendings performing gynecologic surgery) will be identified from the Department of Women's Health at the University of Texas at Austin

Dell Medical School. Surgery days for each enrolled surgeon will be screened for inclusion. Surgery days containing at least one gynecologic surgery with two hours of total operating time in one day are eligible for inclusion. The eligible surgery days will then be randomized to standard surgery days or surgery days with the intervention (microbreaks with exercises).

18 Recruitment Overview

Click on the check box (or double click and type an "X" if using Google Docs) all recruitment methods utilized for this research.

 E-mail	 Flyer
 In-Person	 Letter
 Social Media	 Research Pool
 Telephone/Text	 Snowball Sampling
 Web-post	 Word of Mouth

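### The stated power inputs give 15 surgeons, not 20, by the plan's own Table 1, and the tabulated power is not for the planned exercise versus no-exercise test

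*Combined protocol and SAP*

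**What the plan says.** Section 5, Power analysis, states of G*Power that "we computed the required sample size to detect a medium effect with the specified parameters": power 0.85, alpha 0.05, f = 0.25, "and measurements = 10". It continues: "This yielded a total sample size of at least 20 surgeons", each with 10 intervention days and 10 control days, "with a minimal total of 20 surgery days". Section 15 repeats the inputs and the result. Section 14 says "This study will recruit at least 20 surgeons" and that 10 + 10 days per surgeon is a number "which will yield at least 20 surgery days".

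The table below the text is headed "Table 1. Power and sample size estimations for a within-subject design". Its f = 0.25 column reads 0.62, 0.85, 0.95 and 0.99 for total sample sizes of 10, 15, 20 and 25.

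The primary analysis is in section 5, Statistical Analysis: "We will use linear mixed models to test for an association between BPDS and the targeted micro breaks/exercise intervention across surgery days". The effect sizes cited from an earlier microbreak cohort run from d = 0.00 to d = 0.48. The plan does not state the G*Power test used, the number of groups, the correlation among repeated measures, a sphericity correction or a dropout allowance.

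**The concern.** There are two separate problems and one of wording.

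- **Power and sample size do not match.** The text attaches 20 surgeons to 85% power. The table beneath it attaches 15 to 85% and 20 to 95%. A reader cannot tell which power the trial was sized for, or whether the five extra surgeons are a deliberate margin.
- **The powered test does not look like the planned test.** Ten repeated measurements in a within-subject F test ask whether ten occasions differ (or, with two groups, whether the groups differ over occasions). The trial asks whether exercise days differ from non-exercise days, which is one contrast over 20 days per surgeon. Power for that contrast depends on the correlation between days of the same surgeon and on how much the benefit varies between surgeons. If neither is stated, a null result is hard to interpret.
- **Day count.** Twenty surgery days is the figure for one surgeon, but it is worded as a total.

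**Working it through.** **1. Reproducing Table 1**

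Inputs from section 5: alpha 0.05, m = 10 measurements, f as in the column heads. Assumed, because not stated: correlation rho = 0.5, sphericity, and k = 1 or 2 groups. The repeated-measures F test has

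- lambda = N × m × f² / (1 − rho)
- df1 = m − 1 = 9 and df2 = 9(N − k)

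For f = 0.25, lambda = N × 10 × 0.0625 / 0.5 = 1.25N, so 18.75 at N = 15 and 25 at N = 20.

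| N | Power, k = 1 | Power, k = 2 | Table 1 |
|---|---|---|---|
| 14 | 0.819 | 0.817 | – |
| 15 | 0.853 | 0.850 | 0.85 |
| 19 | 0.939 | 0.938 | – |
| 20 | 0.952 | 0.951 | 0.95 |

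Over the 16 cells with f ≤ 0.25, the largest gap from Table 1 is 0.009 for one group and 0.005 for two. The table is therefore reproduced.

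**2. The stated sample size**

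In both versions the smallest N for 85% power is 15. If a two-group set-up is rounded to equal groups it is 16, with power 0.879. Twenty is the smallest N that reaches 95%. At N = 20 the plan's own method has 85% power for f = 0.21. So 0.85 and 20 are not a matching pair.

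**3. Could Table 1 come from a 1-df test?**

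A two-level intervention has one numerator degree of freedom. Two 1-df tests were fitted to the same 16 cells, with rho searched from 0 to 0.95 in steps of 0.01.

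| Test | Best rho | Largest gap |
|---|---|---|
| Two conditions, within surgeon | 0.79 | 0.057 |
| Two groups, between surgeons, m = 10 | 0 | 0.059 |

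Even with a freely fitted noncentrality, the best 1-df test misses a cell by about 0.05. The table has two decimals in these columns, so rounding cannot explain this.

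**4. Power for the planned contrast**

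For 20 surgeons with 10 + 10 days, let d be the effect in SD units of one day's change in the discomfort index (BPDS), rho the correlation between days of one surgeon, and tau the between-surgeon SD of the effect in the same units. Then

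SE = √[(2(1 − rho)/10 + tau²)/20], with 19 df.

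Example, rho = 0.5 and tau = 0: SE = √(0.1/20) = 0.0707.

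| rho | tau | d for 85% power |
|---|---|---|
| 0.5 | 0 | 0.223 |
| 0.5 | 0.3 | 0.308 |
| 0.5 | 0.5 | 0.418 |
| 0.3 | 0 | 0.264 |
| 0.3 | 0.3 | 0.339 |
| 0.3 | 0.5 | 0.441 |

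For two conditions, f = 0.25 corresponds to d = 2 × 0.25 = 0.50. Power at d = 0.50 runs from 0.924 (rho 0.3, tau 0.5) to above 0.99. At d = 0.24, the midpoint of the cited 0.00 to 0.48, it runs from 0.372 (rho 0.3, tau 0.5) to 0.896 (rho 0.5, tau 0). Simulation gave 0.924, 0.370 and 0.896 for the three values quoted to three decimals.

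**5. Days**

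10 + 10 = 20 per surgeon; 20 surgeons × 20 = 400 surgeon-days.

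**The case against.** The best defence is that nothing here harms the trial. Twenty exceeds 15, the text says at least 20, and the table directly below shows the reader both figures. Some loss is foreseeable: surgeons who are injured must withdraw (item 53), and surgeons without discomfort ratings are excluded from analysis (section 5). A 25% allowance would take 15 to exactly 20 (15/0.75). At the plan's chosen medium effect, the planned contrast has power above 0.85 throughout the range examined.

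Most of that stands as a limit on the consequence. It does not rescue the statement, because the text presents 20 as the result of the listed inputs and no dropout allowance is given. A lower correlation (near 0.3), a sphericity correction (near 0.65) or alpha 0.01 could also lead to about 20, but each would contradict Table 1.

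On the second part, both the 9 df and the 1 df are inferred. The plan names no G*Power test and does not specify its mixed model. The two-group version could be a group-by-time interaction, which would at least involve the intervention. It would still have 9 df and would not test the overall exercise effect.

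The d range rests on assumed values. Widening rho to 0 to 0.8 gives d = 0.14 to 0.47, and power at d = 0.24 from 0.33 to above 0.99. A random-intercept model (about 379 df) would need d = 0.21 instead of 0.22 at rho 0.5 and tau 0. The range is therefore illustrative.

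The day count reads naturally as per surgeon. If two participants share an operating day, 400 counts surgeon-days and not distinct days.

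**Conclusion.** The concern holds. By the plan's own Table 1, the stated inputs give 15 surgeons, and 20 surgeons correspond to about 95% power. This part needs no outside assumption. It errs on the safe side.

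That the tabulated power belongs to a different test is an inference, but a strong one: a 9-df test fits Table 1 within 0.01, and no 1-df test examined comes closer than about 0.05. The plan thus states no power or detectable effect for its primary contrast. Under the assumed correlation of 0.3 to 0.5 and tau of 0 to 0.5, the detectable effect at 85% power is d = 0.22 to 0.44. That is comfortable for d = 0.50 but leaves power anywhere from 0.37 to 0.90 at the middle of the cited range. Underpowering is not shown. This should be fixed before the sample size justification is relied on. The day count is a minor wording point.

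**What to change.** Keep 20 surgeons and 10 + 10 days.

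1. In sections 5 and 15, state that the G*Power inputs give 15 surgeons for 85% power and that 20 give about 95%. Alternatively, correct the stated power, or give the reason for choosing 20, such as a dropout allowance if one was intended.
2. Replace or supplement Table 1 with power for the exercise versus no-exercise contrast in the mixed model, with 10 + 10 days per surgeon. State the assumed within-surgeon correlation and between-surgeon SD of the effect, say whether the model has a random intervention effect, and show a range. The d = 0.22 to 0.44 above can serve as an illustration until the team justifies its own values.
3. If Table 1 stays, name the G*Power test, the number of groups and the correlation.
4. In sections 5, 14 and 15, write 20 surgery days per surgeon, 400 surgeon-days in total.

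The cost is wording in three sections and one short recalculation, with no change to enrolment or conduct.
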